## List of abbreviations

AE	Adverse Event
COVID-19	Coronavirus 2019
CRF	Case Report/Record Form (paper or electronic)
CRO	Contract Research Organization
CTC	Common Terminology Criteria
EDC	Electronic Data Capture
EOS	End of Study
[REDACTED]	[REDACTED]
EU	European Union
FDA	Food and Drug Administration
GCP	Good Clinical Practice
HBV	Hepatitis B Virus
HIV	Human immunodeficiency virus
IB	Investigator's Brochure
ICF	Informed Consent Form
ICH	International Council for Harmonization of Technical Requirements for Pharmaceuticals for Human Use
iDMT	Injectable Disease Modifying Therapy
[REDACTED]	[REDACTED]
IN	Investigator Notification
IND	Investigational New Drug
IRB	Institutional Review Board
IRT	Interactive Response Technology
mg	milligram(s)
ml	milliliter(s)
mAb	monoclonal antibody
QMS	Quality Management System
s.c.	subcutaneous
SAE	Serious Adverse Event
SUSAR	Suspected Unexpected Serious Adverse Reaction

## Glossary of terms

Additional treatment	Medicinal products that may be used during the clinical trial as described in the protocol, but not as an investigational medicinal product (e.g. any background therapy)
Assessment	A procedure used to generate data required by the study
Biologic Samples	A biological specimen including, for example, blood (plasma, serum), saliva, tissue, urine, stool, etc. taken from a study participant
Cohort	A specific group of participants fulfilling certain criteria and generally treated at the same time
Control drug	A study drug (active or placebo) used as a comparator to reduce assessment bias, preserve blinding of investigational drug, assess internal study validity, and/or evaluate comparative effects of the investigational drug
Dosage	Dose of the study treatment given to the participant in a time unit (e.g. 100 mg once a day, 75 mg twice a day)
Electronic Data Capture (EDC)	Electronic data capture (EDC) is the electronic acquisition of clinical study data using data collection systems, such as Web-based applications, interactive voice response systems and clinical laboratory interfaces. EDC includes the use of Electronic Case Report Forms (eCRFs) which are used to capture data transcribed from paper source forms used at the point of care
End of the clinical trial	The end of the clinical trial is defined as the last visit of the last participant or at a later point in time as defined by the protocol
Enrollment	Point/time of participant entry into the study at which informed consent must be obtained
Estimand	A precise description of the treatment effect reflecting the clinical question posed by the trial objective. It summarizes at a population-level what the outcomes would be in the same patients under different treatment conditions being compared. Attributes of an estimand include the population, variable (or endpoint) and treatment of interest, as well as the specification of how the remaining intercurrent events are addressed and a population-level summary for the variable.
Intercurrent events	Events occurring after treatment initiation that affect either the interpretation or the existence of the measurements associated with the clinical question of interest.
Investigational drug/ treatment	The drug whose properties are being tested in the study
Medication number	A unique identifier on the label of medication kits
Mis-enrolled participants	Mis-enrolled participants are those who were not qualified for enrollment and who did not take study treatment, but have been inadvertently enrolled into the study
Other treatment	Treatment that may be needed/allowed during the conduct of the study (i.e. concomitant or rescue therapy)
Part	A sub-division of a study used to evaluate specific objectives or contain different populations. For example, one study could contain a single dose part and a multiple dose part, or a part in participants with established disease and in those with newly-diagnosed disease
Participant	A trial participant (can be a healthy volunteer or a patient)
Participant number	A unique number assigned to each participant upon signing the informed consent. This number is the definitive, unique identifier for the participant and

	should be used to identify the participant throughout the study for all data collected, sample labels, etc.
Period	The subdivisions of the trial design (e.g. Screening, Treatment, Follow-up) which are described in the Protocol. Periods define the study phases and will be used in clinical trial database setup and eventually in analysis
Personal data	Participant information collected by the Investigator that is coded and transferred to Novartis for the purpose of the clinical trial. This data includes participant identifier information, study information and biological samples.
Premature participant withdrawal	Point/time when the participant exits from the study prior to the planned completion of all study drug administration and/or assessments; at this time all study drug administration is discontinued and no further assessments are planned
Participant number	A unique identifier assigned to each screened participant
Screen Failure	A participant who did not meet one or more criteria that were required for participation in the study
Source Data/Document	Source data refers to the initial record, document, or primary location from where data comes. The data source can be a database, a dataset, a spreadsheet or even hard-coded data, such as paper or eSource
Start of the clinical trial	The start of the clinical trial is defined as the signature of the informed consent by the first participant
Study treatment	Any drug or combination of drugs or intervention administered to the study participants as part of the required study procedures; includes investigational drug(s), control(s) or background therapy
Study treatment discontinuation	When the participant permanently stops taking any of the study drug(s) prior to the defined study treatment completion date (if any) for any reason; may or may not also be the point/time of study discontinuation
Treatment arm/group	A treatment arm/group defines the dose and regimen or the combination, and may consist of 1 or more cohorts.
Treatment of interest	The treatment of interest and, as appropriate, the alternative treatment to which comparison will be made. These might be individual interventions, combinations of interventions administered concurrently, e.g. as add-on to standard of care, or might consist of an overall regimen involving a complex sequence of interventions. This is the treatment of interest used in describing the related clinical question of interest, which might or might not be the same as the study treatment.
Variable (or endpoint)	The variable (or endpoint) to be obtained for each participant that is required to address the clinical question. The specification of the variable might include whether the participant experiences an intercurrent event.
Withdrawal of study consent (WoC)	Withdrawal of consent from the study occurs only when a participant does not want to participate in the study any longer and does not allow any further collection of personal data

## **Amendment 2**

### **Amendment Rationale**

This protocol has been amended to allow participants with a known diagnosis of COVID-19 prior to starting in the study to be enrolled. In this amendment we have also addressed inconsistencies and sought to make clarifications at certain points.

### **Changes to the protocol**

Changes to specific sections of the protocol are shown in the track changes version of the protocol using strike through red font for deletions and red underlined for insertions.

### **IRBs/IECs**

A copy of this amended protocol will be sent to the Institutional Review Board (IRBs)/Independent Ethics Committee (IECs) and Health Authorities. The changes herein affect the Informed Consent. Sites are required to update and submit for approval a revised Informed Consent that takes into account the changes described in this protocol amendment.

## **Amendment 1**

### **Amendment Rationale**

This protocol has been amended to add 3 new cohorts comprised of participants who have completed a full course (two doses) of a COVID-19 mRNA vaccine. Also, the sample size of the study is increased to enroll a reasonable number of participants in all six cohorts. Given the decline in the US vaccination rate, the decision to include participants who are fully vaccinated was made to increase the rate in which participants are enrolled and to capture additional data related to mounting an immune response. The number of interim analysis is increased from one to three. In this amendment we have also addressed inconsistencies and sought to make clarifications at certain points.

### **Changes to the protocol**

Changes to specific sections of the protocol are shown in the track changes version of the protocol using strike through red font for deletions and red underlined for insertions.

### **IRBs/IECs**

A copy of this amended protocol will be sent to the Institutional Review Board (IRBs)/Independent Ethics Committee (IECs) and Health Authorities. The changes herein affect the Informed Consent. Sites are required to update and submit for approval a revised Informed Consent that takes into account the changes described in this protocol amendment.

## Protocol summary

Protocol number	COMB157GUS16														
Full Title	An open-label multicenter study to assess response to COVID-19 vaccine in participants with multiple sclerosis treated with ofatumumab 20 mg subcutaneously														
Brief title	A multicenter study to assess response to COVID-19 vaccine in multiple sclerosis participants treated with ofatumumab														
Sponsor and Clinical Phase	Novartis Clinical phase IV														
Investigation type	Biological/Vaccine														
Study type	Interventional, 6-cohort														
Purpose and rationale	The objective of this study is to assess whether participants treated with ofatumumab 20 mg subcutaneous (s.c.) administered once monthly can mount an adequate immune response to non-live COVID-19 mRNA vaccine as measured by humoral responses compared to participants on an interferon or glatiramer acetate.														
Primary Objective(s)	To assess immune response to non-live mRNA COVID-19 vaccine in ofatumumab treated subjects														
Secondary Objectives	
 
To assess immune conversion to non-live mRNA COVID-19 vaccine in ofatumumab treated subjects
 
To assess adverse events and serious adverse events
 
														
Study design	
This is a 6-cohort, multicenter, prospective study of up to 88 relapsing MS participants.
 
  
 Cohort	Brief Description	
   
 1	Vaccine naive, planning to start OMB	
 
 2	Vaccine naive, currently on OMB for <math>\geq</math> 4 weeks	
 
 3	Vaccine naive, on interferon or glatiramer acetate for <math>\geq</math> 4 weeks	
 
 4	Fully vaccinated, currently on OMB for <math>\geq</math> 4 weeks	
 
 5	Fully vaccinated, on interferon or glatiramer acetate for <math>\geq</math> 4 weeks, +/- booster	
 
 6	Fully vaccinated, currently on OMB for <math>\geq</math> 4 weeks, + booster	
  
 
All groups will undergo serologic testing.
 
Participants will obtain the COVID-19 mRNA vaccine from their HCP (private insurance) or appropriate federal, state or local program.
	Cohort	Brief Description	1	Vaccine naive, planning to start OMB	2	Vaccine naive, currently on OMB for $\geq$ 4 weeks	3	Vaccine naive, on interferon or glatiramer acetate for $\geq$ 4 weeks	4	Fully vaccinated, currently on OMB for $\geq$ 4 weeks	5	Fully vaccinated, on interferon or glatiramer acetate for $\geq$ 4 weeks, +/- booster	6	Fully vaccinated, currently on OMB for $\geq$ 4 weeks, + booster
Cohort	Brief Description														
1	Vaccine naive, planning to start OMB														
2	Vaccine naive, currently on OMB for $\geq$ 4 weeks														
3	Vaccine naive, on interferon or glatiramer acetate for $\geq$ 4 weeks														
4	Fully vaccinated, currently on OMB for $\geq$ 4 weeks														
5	Fully vaccinated, on interferon or glatiramer acetate for $\geq$ 4 weeks, +/- booster														
6	Fully vaccinated, currently on OMB for $\geq$ 4 weeks, + booster														
Study population	Adult (ages 18-55) relapsing MS participants														
Key Inclusion criteria	
Patients eligible for inclusion in Cohort 1 of this study must fulfill the following criteria:
 
 
1. Signed informed consent must be obtained prior to participation in the study
 
2. Age 18-55 years old inclusive at Screening
 
3. Diagnosis of relapsing MS by 2017 revised McDonald criteria
 
4. Must be willing to comply with the study schedule
 
														

	

5. Will be receiving an mRNA COVID-19 vaccine (Pfizer or Moderna vaccine)

6. Eligible to receive and plan to be started on Ofatumumab according to the approved labeling

7. Pre-ofatumumab serologies with Hepatitis B testing not indicative of active or latent infection

8. Total serum immunoglobulin IgG <math>\geq 400</math> mg/dl at Screening

 
Patients eligible for inclusion in Cohort 2 of this study must fulfill the following criteria:
 

1. Signed informed consent must be obtained prior to participation in the study

2. Age 18-55 years old at Screening

3. Diagnosis of relapsing MS by 2017 revised McDonald criteria

4. Must be willing to comply with the study schedule

5. Currently on commercially prescribed ofatumumab for <math>\geq 4</math> weeks for the treatment of RMS

6. Will be receiving an mRNA COVID-19 vaccine (Pfizer or Moderna vaccine)

7. Pre-ofatumumab serologies with Hepatitis B testing not indicative of active or latent infection

8. Total serum immunoglobulin IgG <math>\geq 400</math> mg/dl at Screening

 
Patients eligible for inclusion in Cohort 3 of this study must fulfill the following criteria:
 

1. Signed informed consent must be obtained prior to participation in the study

2. Age 18-55 years old at Screening

3. Diagnosis of relapsing MS by 2017 revised McDonald criteria

4. Must be willing to comply with the study schedule

5. Currently on commercially prescribed interferon or glatiramer acetate for <math>\geq 4</math> weeks for the treatment of RMS

6. Will be receiving an mRNA COVID-19 vaccine (Pfizer or Moderna vaccine)

7. Total serum immunoglobulin IgG <math>\geq 400</math> mg/dl at Screening

 
Patients eligible for inclusion in Cohort 4 of this study must fulfill the following criteria:
 

1. Signed informed consent must be obtained prior to participation in the study

2. Age 18-55 years old at Screening

3. Diagnosis of relapsing MS by 2017 revised McDonald criteria

4. Must be willing to comply with the study schedule

5. Completed a full course (two doses) of a COVID-19 mRNA vaccine at least <math>\geq 4</math> weeks after start of commercially prescribed ofatumumab for the treatment of RMS

6. Currently on commercially prescribed ofatumumab for <math>\geq 4</math> weeks for the treatment of RMS

7. Received two dose mRNA COVID-19 vaccine (Pfizer or Moderna vaccine) <math>\geq 2</math> weeks ago

8. Pre-ofatumumab serologies with Hepatitis B testing not indicative of active or latent infection

9. Total serum immunoglobulin IgG <math>\geq 400</math> mg/dl at Screening

 
Patients eligible for inclusion in Cohort 5 of this study must fulfill the following criteria:
 

1. Signed informed consent must be obtained prior to participation in the study

2. Age 18-55 years old at Screening

3. Diagnosis of relapsing MS by 2017 revised McDonald criteria

4. Must be willing to comply with the study schedule

5. Currently on commercially prescribed interferon or glatiramer acetate for <math>\geq 4</math> weeks for the treatment of RMS

--	--

	
6. Completed a full course (two doses) of a COVID-19 mRNA vaccine after start of glatiramer acetate or interferon
 
7. Received two dose mRNA COVID-19 vaccine (Pfizer or Moderna vaccine) <math>\geq</math> 2 weeks ago
 
8. If the patient has received the mRNA booster, then the mRNA booster should be <math>\geq</math> 2 weeks prior to enrollment
 
9. Total serum immunoglobulin IgG <math>\geq</math> 400 mg/dl at Screening
 
Patients eligible for inclusion in Cohort 6 of this study must fulfill the following criteria:
 
 
1. Signed informed consent must be obtained prior to participation in the study
 
2. Age 18-55 years old at Screening
 
3. Diagnosis of relapsing MS by 2017 revised McDonald criteria
 
4. Must be willing to comply with the study schedule
 
5. Currently on commercially prescribed ofatumumab
 
6. Completed a full course (two doses) of a COVID-19 mRNA vaccine at least <math>\geq</math> 4 weeks after start of commercially prescribed ofatumumab for the treatment of RMS
 
7. Received two dose mRNA COVID-19 vaccine (Pfizer or Moderna vaccine) <math>\geq</math> 2 weeks ago
 
8. Pre-ofatumumab serologies with Hepatitis B testing not indicative of active or latent infection
 
9. Total serum immunoglobulin IgG <math>\geq</math> 400 mg/dl at Screening
 
10. Has received an mRNA booster <math>\geq</math> 2 weeks prior to enrollment
 

Key Exclusion criteria	
 
1. Already has received the J&J vaccine.
 
2. Has a contraindication to receiving an mRNA COVID-19 vaccine
 
3. Has an immediate allergic reaction to a past vaccine or injection
 
4. Any safety finding including low immunoglobulin IgG and/or low immunoglobulin IgM levels requiring an ofatumumab treatment interruption within the 12 weeks immediately prior to vaccination as determined by the HCP
 
5. Any major episode of infection requiring hospitalization or treatment with intravenous antibiotics within 4 weeks prior to the first vaccination visit or oral antibiotics within two weeks prior to the first vaccination visit
 
6. Prior treatment with B-cell targeted therapies (e.g., rituximab or ocrelizumab), alemtuzumab, anti-CD4, cladribine, cyclophosphamide, mitoxantrone, azathioprine, mycophenolate mofetil, cyclosporine, methotrexate, total body irradiation, or bone marrow transplantation
 
7. Prior treatment with S1P agent within 2 months at Screening
 
8. Prior treatment with natalizumab within 6 months of study enrollment/Visit 2
 
9. Since commercially prescribed ofatumumab is being used in the study, contraindications as per the USPI will be adhered to which include active infection hepatitis B infection, progressive multifocal leukoencephalopathy and pregnancy
 
10. Participation in another interventional clinical trial within 14 days before enrollment
 

Study treatment	
Participants in Cohort 1 (Pfizer vaccine): The first of three 20 mg sc ofatumumab loading doses will be administered on Day 36 or 2 weeks after receiving a full course (two doses) of COVID-19 vaccine. The 2nd and 3rd loading doses should be administered on Day 43 and Day 50 or 7 and 14 days respectively after the 1st loading dose. Subsequent dosing includes 20 mg sc administered monthly starting at Day 64.

	
Participants in Cohort 1 (Moderna vaccine): The first of three 20 mg sc ofatumumab loading doses will be administered on Day 43 or 2 weeks after receiving a full course (two doses) of COVID-19 vaccine. The 2nd and 3rd loading doses should be administered on Day 50 and Day 57 or 7 and 14 days respectively after the 1st loading dose. Subsequent dosing includes 20 mg sc administered monthly starting at Day 71.
 
Participants in Cohort 2: Will continue to take prescribed ofatumumab as per their current dosing schedule.
 
Participants in Cohort 3: Will continue to take interferon or glatiramer acetate as per their current dosing schedule.
 
Participants in Cohort 4: Will continue to take prescribed ofatumumab as per their current dosing schedule.
 
Participants in Cohort 5: Will continue to take prescribed glatiramer acetate or interferon as per their current dosing schedule.
 
Participants in Cohort 6: Will continue to take prescribed ofatumumab as per their current dosing schedule.

Treatment of interest	COVID-19 mRNA vaccine
Efficacy assessments	None
Key safety assessments	

• SARS-CoV-2 qualitative/quantitative IgG antibody assay

• Adverse events/serious adverse events

 
Data analysis	
The primary endpoint is achieving immune response as defined by a positive SARS-CoV-2 qualitative IgG antibody assay 14 days after full course (two doses) vaccination (yes/no).
 
The sample size of 20 participants per individual or combined cohort is selected based on budget and need for early availability of results. The sample size of 20 participants will provide estimates with margin of error (half-width of a 95% confidence interval) of 20.1%, 19%, and 17.5% corresponding to immune response rates of 70%, 75%, and 80%, respectively. Adjusting for 10% drop-out, 22 participants will be enrolled in Cohort 1. In combination, 22 participants will be enrolled in Cohorts 2 and 4. In combination, 22 patients will be enrolled in Cohorts 3 and 5. In Cohort 6, 22 participants will be enrolled.
 
The number and percentage of responders will be presented. The 95% confidence interval for the proportion of responders will be calculated by using exact method.

Key words	COVID-19, vaccine, ofatumumab, SARS-CoV2, antibody,  open-label

## 1 Introduction

### 1.1 Background

Multiple sclerosis (MS) is a common cause of neurologic disability in young adults. In this disease, damage is caused by an autoimmune attack of the central nervous system. Recent phase 3 trials have demonstrated that antibodies that bind and cause CD20 B cells apoptosis have a powerful anti-inflammatory effect as measured by relapse and MRI activity, and leave participants with less disability than active comparators ([Hauser et al 2020](#) and [Hauser et al 2017](#)).

MS disease modifying treatments target the immune system and in so doing may diminish vaccine efficacy ([Farez et al 2019](#)). Questions have arisen whether therapies that affect B cells might also abrogate vaccine response. Though other medications also impact B cells, anti-CD20 antibodies have the most selective and potent impact on B cells. These antibodies impact memory B cells which are believed to be an important component in maintaining immunologic memory but also preserve immunoglobulin secreting plasma cells which function to recognize and remove pathogens. Research with an anti-CD20 B cell agent, ocrelizumab, indicates that an immune response can occur after vaccination but that the proportion of participants with an adequate response is diminished relative to a control group ([Bar-Or et al 2020](#)).

Ofatumumab is a subcutaneously administered anti-CD20 therapy that received FDA approval for treatment of relapsing forms of MS in August 2020. Data is currently lacking regarding whether MS participants on ofatumumab can mount an appropriate immune response to vaccines, including the COVID-19 vaccine. In this study, MS participants will receive the COVID-19 vaccination and follow-up assays to assess whether they are able to mount a response to the vaccine. A reference cohort of participants on injectable disease modifying treatments (interferon or glatiramer acetate) is included. In a prior study, interferon and glatiramer acetate did not diminish vaccine response ([Olberg et al 2018](#)).

### 1.2 Purpose

An important safety concern for health care providers and patients is whether an MS disease modifying agent might compromise vaccine efficacy. Ofatumumab is a human anti-CD20 monoclonal antibody (mAb) that induces B-cell depletion. An increased risk of infections has been observed with other anti-CD20 B-cell depleting therapies. Ofatumumab has the potential for an increased risk of infections, including serious bacterial, fungal, and new or reactivated viral infections; some of these infections have been fatal in patients treated with other anti-CD20 antibodies. As such, participants on ofatumumab may have an increased risk of morbidity and mortality should they contract COVID-19. Therefore, it is important to assess if participants treated with ofatumumab are able to mount protective immune responses against the COVID-19 vaccine.

This study will aim to address the following:

1. To define COVID vaccine response in patients receiving a full course mRNA vaccination and how treatment with ofatumumab effects response.
2. To determine the impact of a booster dose on immune response.

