## 12.8 Sample size calculation

### 12.8.1 Primary endpoint(s)

The sample size of 20 participants per cohort is selected based on budget and need for early availability of results. This sample size of 20 participants will provide estimates of proportion of responders with margin of error (half-width of a 95% confidence interval) of 20.1%, 19%, and 17.5% corresponding to response rates of 70%, 75%, and 80%, respectively. Adjusting for 10% drop-out, 22 participants will be enrolled in Cohort 1. In combination, 22 participants will be enrolled in Cohorts 2 and 4. In combination, 22 patients will be enrolled in Cohorts 3 and 5. In Cohort 6, 22 participants will be enrolled.

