1.2.1 Primary estimand(s)

The estimand is the precise description of the treatment effect and reflects strategies to address events occurring during the trial conduct which could impact the interpretation of the trial results (e.g., premature discontinuation of treatment).

The primary clinical question of interest is: Do relapsing MS participants who receive ofatumumab treatment mount an immune response to non-live mRNA COVID-19 vaccine?

The justification for the primary estimand is that it will capture whether ofatumumab-treated participants generate antibodies to mRNA COVID-19 vaccines.

The primary estimand is described by the following attributes:

- **Population:** Defined through appropriate inclusion/exclusion criteria to reflect the targeted population. Relapsing MS participants subdivided into 6 cohorts. (1) Will receive a full course (2 doses) of a COVID-19 mRNA vaccine \geq 2 weeks prior to starting ofatumumab 20 mg s.c. treatment; (2) Will receive a full course (2 doses) of a COVID-19 mRNA vaccine after \geq 4 weeks of commercial ofatumumab 20 mg s.c. treatment (3) Will receive a full course (2 doses) of a COVID-19 mRNA vaccine after \geq 4 weeks of interferon or glatiramer acetate treatment (4) Completed a full course (2 doses) of a COVID-19 mRNA vaccine after \geq 4 weeks of commercial ofatumumab 20 mg s.c. treatment but has not yet received a COVID-19 mRNA booster (5) Completed a full course (2 doses) of a COVID-19 mRNA vaccine after \geq 4 weeks of interferon or glatiramer acetate (may or may not have received a COVID-19 mRNA booster) (6) Completed a full course (2 doses) of a COVID-19 mRNA vaccine after \geq 4 weeks of commercial ofatumumab 20 mg s.c. treatment and received an additional booster vaccine \geq 14 days prior to screening
- **Variable:** Achieving immune response as defined by a positive SARS-CoV-2 qualitative IgG antibody assay \geq 14 days after full course (2 doses) vaccination (yes/no)

- **Treatment of interest:** Non-live COVID-19 mRNA vaccine either ≥ 2 weeks prior to ofatumumab start or ≥ 4 weeks after ofatumumab start or while on interferon or glatiramer acetate
- **Intercurrent event:** Discontinuation of treatment/study, or death
- **Summary measure:** Proportion of participants achieving immune response

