2.5.2 Statistical hypothesis, model, and method of analysis

The number and percentage of responders will be presented by cohort group and overall. The 2-sided 95% CI for the proportion of responders will be calculated using an exact method ([Clopper and Pearson, 1934](#)).

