2.5.6 Supplementary analyses

A supplemental analysis of the primary endpoint will be performed using an observed case approach (completers) by using valid assessments of antibody assay without imputation of missing data.

In addition, the primary analysis will be repeated using data from Cohort 6 participants and any participants in Cohorts 1 – 5 who received an mRNA booster during the study. Missing post-vaccination antibody assay will be handled according to the NRI approach.

For each supplemental analysis the number and percentage of responders will be presented by cohort group and overall. The 2-sided 95% CI for the proportion of responders will be calculated using an exact method ([Clopper and Pearson, 1934](#)).

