5.4 Statistical models

5.4.1 Analysis supporting primary objective(s)

There is no hypothesis testing planned for the analysis supporting the primary objective of this study.

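### Aim 2, the impact of a booster, has no effect measure in the visible plan, and the only booster analysis keeps second-dose timing in Cohorts 1 to 5, so it can count pre-booster samples

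*Protocol*

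**What the plan says.** Protocol 1.2 lists two aims, the second being "To determine the impact of a booster dose on immune response". Table 2-1 of the protocol and Table 1 of the SAP contain no booster objective or endpoint, and the two design questions in protocol 4.1 do not mention a booster. The estimand variable (SAP 1.2.1) is a "positive SARS-CoV-2 qualitative IgG antibody assay" at least 14 days after the two-dose course, and the summary measure is a proportion.

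SAP 2.5.2 states: "The number and percentage of responders will be presented by cohort group and overall". It adds: "The 2-sided 95% CI for the proportion of responders will be calculated using an exact method". SAP 5.4.1 says: "There is no hypothesis testing planned for the analysis supporting the primary objective of this study".

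Boosters are not ignored. Protocol 12.5 sets boosted participants apart for further analysis without giving a method. SAP 2.5.6 says "the primary analysis will be repeated using data from Cohort 6 participants and any participants in Cohorts 1" to 5 who were boosted during the study, by cohort group and overall. SAP 2.6.6 does the same for the secondary endpoints. SAP 2.4.1.1 starts the first window for Cohort 6 the day after its booster; for Cohorts 1 to 5 the anchor is the second dose. SAP 1.1 sets the primary time point at Visit 4 for Cohorts 1 to 3 and Visit 2 for Cohorts 4 to 6.

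**The concern.** The word impact implies a reference: boosted against unboosted, or after against before. Every visible output is instead a proportion in one group with its own interval. Readers who want the booster effect will subtract two separately reported rates, or judge by whether two intervals overlap, with no stated precision for the difference.

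The timing matters more. A table headed as the booster analysis should hold post-booster results. Repeating the primary analysis in Cohorts 1 to 5 without moving the time point does not ensure that. Its overall row would then mix post-booster results from Cohort 6 with results taken before the booster in everyone else. The before-and-after assays that on-study boosters would supply are not paired in any visible table.

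**Working it through.** **1. Where the primary result comes from (SAP 1.1 and SAP Tables 2, 5 and 8; days are Pfizer / Moderna).**

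| Group | Primary visit | First antibody window | Next scheduled assay |
|---|---|---|---|
| Cohort 1 | Visit 4, Day 36 / 43 | second dose + 1 to Day 64 / 71 | Day 92 / 99 |
| Cohorts 2, 3 | Visit 4, Day 36 / 43 | second dose + 1 to Day 119 / 126 | Day 202 / 209 |
| Cohorts 4, 5 | Visit 2, Day 1 | second dose + 1 to Day 1 | Day 202 / 209 |
| Cohort 6 | Visit 2, Day 1 | booster + 1 to Day 1 | Day 202 / 209 |

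In Cohorts 4 and 5 the window closes on Day 1, so no assay after a later booster can enter it. In Cohorts 1 to 3, the first scheduled assay after Visit 4 already falls in a later window. Only an unscheduled assay could land in the first one, and SAP 2.4.1.1 then takes the worst result for a categorical variable, so a pre-booster negative would still stand.

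**2. Example (booster day assumed).** A Cohort 4 Pfizer participant is negative on Day 1, boosted on Day 100 and positive on Day 202. The repeated primary analysis in SAP 2.5.6 includes this person and counts the Day 1 negative. The Day 202 result appears only in the by-visit repeat under SAP 2.6.6, labelled as 180 days after vaccination, beside results from people not yet boosted by that visit. A paired table would show negative before, positive after, with 202 − 1 = 201 days between assays.

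**3. How much of the table could be affected.** Cohorts 1 to 5 hold 88 − 22 = 66 participants. If m of them are boosted on study after their primary visit, the pre-booster share of the overall row is m / (22 + m). The documents give no m, so these values are assumptions: m = 10 gives 10/32 = 31%; m = 33 gives 33/55 = 60%; m = 66 gives 66/88 = 75%.

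**4. Precision of a between-cohort contrast.** The plan's own figures come first. Protocol 12.8.1 gives margins of "20.1%, 19%, and 17.5% corresponding to response rates of 70%, 75%, and 80%, respectively". With n = 20, 1.96 × √(p(1 − p)/20) gives 20.1, 19.0 and 17.5 points, so they reproduce as normal-approximation half-widths for one proportion. The planned exact interval is a little wider: 21.2, 20.2 and 19.0 points at 14, 15 and 16 of 20.

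For a difference between two groups of 20 with equal rates p, the half-width is 1.96 × √(2p(1 − p)/20):

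- p = 70%: 1.96 × √0.0210 = 28.4 points (Newcombe 26.8)
- p = 75%: 1.96 × √0.01875 = 26.8 points (Newcombe 25.9)
- p = 80%: 1.96 × √0.0160 = 24.8 points (Newcombe 24.7)

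Newcombe combines the Wilson limits of the two groups: d − √((p₂ − l₂)² + (u₁ − p₁)²) to d + √((u₂ − p₂)² + (p₁ − l₁)²). For 14/20 against 16/20 the Wilson limits are 0.481 to 0.854 and 0.584 to 0.919. The difference is +10 points, with interval −16.6 to +34.9.

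If all 22 per group are counted, as non-response imputation implies, the normal-approximation half-widths become 27.1, 25.6 and 23.6 points. An assumed 17/22 (77%) against 12/22 (55%) gives +22.7 points, −5.1 to +46.3; 55% lies outside the plan's own rates.

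**The case against.** Several stronger readings are tempting, and the documents do not support them.

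- A reader might infer that boosters are not analysed, or that Cohort 6 is simply reported alone. Protocol 12.5 and SAP 2.5.6 and 2.6.6 do plan a booster set.
- A reader might infer that Cohort 6 is assessed on a two-dose result. That is true of the variable's wording only. Its booster precedes entry by at least 14 days and its window starts after the booster, so its Visit 2 sample is already post-booster.
- A reader might infer that aim 2 cannot be addressed at all. The study is explicitly for estimation, and separate proportions for Cohort 6 and for Cohorts 2 and 4 allow a crude side-by-side reading. A difference can be computed from published counts; printing it is partly a matter of presentation.
- A reader might infer that the within-person data are free of bias. They remove between-cohort confounding but not waning or intervening infection. Nucleocapsid antibody is scheduled only at Visit 2 in Cohorts 4 to 6 and does not appear in the visible schedules for Cohorts 2 and 3. Scheduled assays around a later booster can be 90 to about 200 days apart.

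Protocol 12.6 and SAP 2.12 are also not visible, and neither are some SAP window tables, so statements of absence can cover the visible text only.

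All of this stands, and it narrows the point. It does not answer the timing problem: SAP 2.5.6 is visible, and as written it draws Cohort 1 to 5 results from a visit that may precede the booster.

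**Conclusion.** The point holds in a limited form. In the visible text, aim 2 has no endpoint, estimand or effect measure. Its only analysis is a supplementary one-sample proportion that is not timed to the booster in Cohorts 1 to 5. Anyone there boosted after Visit 4 (Cohorts 1 to 3) or Visit 2 (Cohorts 4 and 5) contributes a pre-booster result to the repeated primary analysis. The number affected is unknown and could be small.

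The primary analysis itself is untouched. The between-cohort contrast would be imprecise, with a half-width of about 25 to 28 points at 20 evaluable per group against the stated 17.5 to 20.1 points for one group. This assumes both true rates lie between 70% and 80%. It should be corrected before database lock, because one of two stated aims otherwise rests on a table that can misdescribe its own content.

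**What to change.** Amend SAP 2.5.6, and 2.6.6 to match:

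1. For Cohort 1 to 5 participants boosted on study, use the first assay at least 14 days after the booster. Tabulate it against the last assay before the booster in a 2 × 2 table by MS treatment, with an exact 95% interval for conversion among those negative before it. State that the number boosted is not planned, that assays are months apart, and that waning or intervening infection cannot be excluded.
2. Report Cohort 6 minus Cohorts 2 and 4 combined at the primary time point with a Newcombe 95% interval, labelled descriptive, unadjusted and non-randomised. Note that time since the last dose differs between these groups.
3. Align the wording of the Cohort 6 variable with its booster-anchored window. This should change no eligible participant's result.

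If the sponsor declines the contrast in item 2, reword aim 2 as describing response in boosted participants. Item 1 is still needed, because the existing supplementary analysis has the timing problem either way.

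The cost is about one SAP paragraph and two tables, with no new visits, samples or tests. The downside is that the paired table may hold few people and the difference will be wide and confounded; both need saying beside the numbers.
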